- Intolerance: Including, but not limited to, infusion- or injection-related reaction, demyelination, congestive heart failure, infection, or any other related adverse event that led to a reduction in dose or discontinuation of the medication

Note: To be considered inadequate response, loss of response, and intolerance after treatment with a biologic or JAK inhibitor, the participant should have received a dosing regimen consistent with the local product labeling, local guidelines for the treatment of UC and/or institutional standard of care.

Concomitant treatments:

9. Participants are permitted to be receiving a therapeutic dose of the following drugs: Oral 5-ASA compounds provided the dose has been stable for ≥ 2 weeks immediately prior to randomization

- Oral corticosteroid therapy (prednisone at a stable dose ≤ 20 mg/day or equivalent steroid) provided the dose has been stable for the 4 weeks immediately prior to the screening endoscopy assessment
- Thiopurines such as oral AZA or 6-MP must be discontinued ≥ 2 weeks prior to randomization
- Probiotics (eg, *Saccharomyces boulardii*) provided the dose has been stable for the 2 weeks immediately prior to randomization

If oral 5-ASA or corticosteroids have been recently discontinued, they must have been stopped for at least 2 weeks prior to the endoscopy used for the baseline MMS.

Other general inclusion criteria:

10. Adequate hematological function defined by white blood cell count $\geq 3.5 \times 10^9/L$ with ANC $\geq 1.5 \times 10^9/L$, lymphocyte count $\geq 0.8 \times 10^9/L$, platelet count $\geq 100 \times 10^9/L$, and hemoglobin $\geq 8 \text{ g/dL}$

11. Adequate hepatic function defined by a total bilirubin level $\leq 1.5 \times$ the upper limit of normal (ULN) range and aspartate aminotransferase (AST) and alanine aminotransferase (ALT) levels $\leq 2.0 \times$ ULN. Participants with an isolated total bilirubin and normal AST and ALT diagnosed with Gilbert's syndrome may participate

12. Adequate renal function defined by an estimated glomerular filtration rate $\geq 30 \text{ mL/min/1.73 m}^2$ by the Chronic Kidney Disease Epidemiology Collaboration equation at screening

13. Females must meet either a or b of the following criteria and males must meet criterion c to qualify for the study:

- a. A female who is not of childbearing potential must meet 1 of the following:
 - Postmenopausal, defined as no menses for 12 months without an alternative medical cause

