10.11. Safety Endpoints

- Incidence and severity of adverse events
- Incidence and severity of laboratory abnormalities, and change from baseline in laboratory values (to include hematology, serum chemistry, coagulation, and urinalysis)
- Incidence of clinically significant vital sign abnormalities and changes from baseline

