#### 18.3.1. Safety Laboratory Evaluations

Hematology, serum chemistry, coagulation, and urinalysis are analysed and reported by central laboratory and sometimes by local laboratory. Results out of reference range are flagged by the performing laboratory (eg, low, high). A full list of laboratory assessments to be included in the outputs is included in Clinical Study Protocol APD334-203 Table 6.

In general, presentations will use Système international d'Unités (SI units). Quantitative laboratory measurements reported as "< X" or "> X", where X may be the lower limit of quantitation (LLQ) or the upper limit of quantitation (ULQ), respectively, will be converted to X for the purpose of quantitative summaries, but will be presented as recorded, ie, as "< X" or "> X" in the listings. For urinalysis, only pH and specific gravity are considered as quantitative tests. If local and central laboratory assessments are available from the same day, central laboratory assessments will be used in the summary as per Section 6.4.

The following summaries will be provided for laboratory data:

- Value and change from Baseline by visit (for hematology, serum chemistry, quantitative urinalysis [pH and specific gravity], coagulation, and high-sensitivity C-reactive protein [hs-CRP])
- Incidence of abnormal values according to laboratory reference ranges by visit
- Incidence of lymphocytes  $< 0.2 \times 10^9/L$ ,  $0.5 \times 10^9/L$ , or neutrophils  $< 0.5 \times 10^9/L$ ,  $1 \times 10^9/L$  at end of treatment and anytime in the study
- Shift from end of treatment to each follow-up visit in incidence of lymphocytes in normal range and in incidence of lymphocytes of at least 80% percent of Baseline, by visit (2-Week Follow-Up, 4-Week Follow-Up, and Last Follow-Up)

Document: \\quintiles.net\enterprise\Apps\sasdata\SASb\SAS\Arena\APD334\RZA28116\Biostatistics\Documenta

tion\SAP\503-Final SAP v2.0\APD334-203 SAP Final v2.0-20231120 clean.docx

Version Number: 2.0 Author: PPD

> Version Date: 20Nov2023

Template No.: CS\_TP\_BS016 Revision 7 Reference: CS WI BS005

Effective Date: 01Nov2021

Page 45 of 70

- Shift from Baseline to end of treatment according to laboratory reference range (for quantitative measurements and categorical measurements)
- Evaluation of drug-induced serious hepatotoxicity (eDISH) plots for the following laboratory assessments (using values after the first administration of study treatment):

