  - Maximum aspartate aminotransferase (AST) versus same-day total bilirubin
  - o Maximum alanine aminotransferase (ALT) versus same-day total bilirubin
  - Maximum gamma-glutamyl transferase (GGT) versus same-day total bilirubin
  - Maximum alkaline phosphatase (ALP) versus same-day total bilirubin

The eDISH plots above will be repeated with adjustment for elevated baseline.

- Incidence of hepatic enzyme elevations by visit
  - $\circ$  > 1 ×, 2 ×, 3 ×, 5 ×, 8 ×, 10 ×, 20 × upper limit of normal (ULN) elevation in ALT
  - >1 ×, 2 ×, 3 ×, 5 ×, 8 ×, 10 ×, 20 × ULN elevation in AST
  - > 3 ×, 5 ×, 10 ×, 20 × ULN elevation in either ALT or AST
  - o > 1 x, 1.5 x, 2 x, 3 x ULN elevation in total bilirubin
  - > 1 ×, 1.5 ×, 2 ×, 3 ×, 5 ×, 8 × ULN elevation in ALP
  - o > 1 ×, 2 ×, 3 ×, 5 ×, 8 × ULN elevation in GGT
  - > 3 × ULN elevation in either ALT or AST and > 1.5 × ULN elevation in total bilirubin
  - 3 × ULN elevation in either ALT or AST and > 2 × ULN elevation in total bilirubin
  - > 3 × ULN elevation in either ALT or AST and > 1.5 × ULN elevation in ALP
  - > 3 × ULN elevation in either ALT or AST in temporal association with treatment-emergent nausea, vomiting, anorexia, abdominal pain, or fatigue identified by PT, where temporal association is defined as ±14 days of onset date from the time of elevation.

If both central and local assessments of total bilirubin are available on the same day, the central result will take precedence over the local result in the eDISH plot. If the maximum AST, ALT, GGT, or ALP assessment occurs at 2 different dates, the assessment with the higher accompanying Bilirubin value will be used. Two versions of the eDISH plots will be presented, with one showing values as multiples of ULN, and the other one showing values as multiples of ULN, or subject's baseline, whichever is higher.

All laboratory tests will be listed. Subject's laboratory assessments at all timepoints will be listed in chronological order. Values outside of the laboratory reference range will be flagged. Values obtained from local laboratory will be flagged. Listing of lymphocytes and neutrophils over time in participants who ever had lymphocytes  $< 0.5 \times$ 

Document: \quintiles.net\enterprise\Apps\sasdata\SASb\SAS\Arena\APD334\RZA28116\Biostatistics\Documenta

tion\SAP\503-Final SAP v2.0\APD334-203 SAP Final v2.0-20231120 clean.docx

Author: PPD Version Number: 2.0

Version Date: 20Nov2023

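### Laboratory severity is part of a protocol safety endpoint, but outside a short list of tests SAP 18.3.1 tabulates only in or out of reference range

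*Protocol*

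**What the plan says.** Protocol 10.11, repeated in the synopsis, lists as a safety endpoint "Incidence and severity of laboratory abnormalities, and change from baseline in laboratory values (to include hematology, serum chemistry, coagulation, and urinalysis"). It therefore asks for three things across four panels: how often abnormalities occur, how severe they are, and how values change.

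SAP 18.3.1 plans three general laboratory summaries:
- "Value and change from Baseline by visit (for hematology, serum chemistry", with quantitative urinalysis, coagulation and hs-CRP also covered).
- "Incidence of abnormal values according to laboratory reference ranges by visit".
- "Shift from Baseline to end of treatment according to laboratory reference range (for quantitative measurements and categorical measurements").

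Two groups of tests get more. Lymphocytes are counted below 0.2 and 0.5 × 10⁹/L and neutrophils below 0.5 and 1 × 10⁹/L, "at end of treatment and anytime in the study". The liver tests ALT, AST, total bilirubin, ALP and GGT get tiered multiples of ULN under "Incidence of hepatic enzyme elevations by visit". Allowance for an abnormal starting value appears only in the liver plots: "The eDISH plots above will be repeated with adjustment for elevated baseline".

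SAP 3.3 lists the departures from the protocol analysis. Laboratory severity is not among them.

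**The concern.** An in-or-out classification records that a value is abnormal but not by how much. This matters most for participants who are already abnormal at entry, and the protocol admits them. Inclusion criterion 10, beginning "Adequate hematological function defined by white blood cell count", allows hemoglobin from 8 g/dL and platelets from 100 × 10⁹/L. Criterion 11 allows total bilirubin up to 1.5 × ULN, and criterion 12 allows an estimated glomerular filtration rate from 30 mL/min/1.73 m².

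For a test without tiers, such a participant is out of range before the first dose. Further movement in the same direction leaves both abnormality tables unchanged. The shift table also stops at end of treatment, so a value that worsens mid-study and recovers does not enter it. At stake is the severity half of a stated safety endpoint: the number of participants per treatment group at each level of severity is not planned for most tests.

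**Working it through.** The point rests on no power, alpha or sample-size figure, so there is no plan figure to reproduce. Three checks apply.

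**1. How many tests have a severity tabulation.** The items are counted from Protocol Table 5, taking WBC with differential as one item and TBNK as one.

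| Panel | Items | With tiers in SAP 18.3.1 |
|---|---|---|
| Hematology | 9 | 1 (WBC differential: lymphocytes and neutrophils only) |
| Serum chemistry | 23 | 4 (ALT, AST, total bilirubin, ALP) |
| Coagulation | 3 | 0 |
| Urinalysis | 12 | 0 |
| Total | 47 | 5 |

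GGT has tiers in the SAP but is not in Table 5. Items without tiers: 47 − 5 = 42, or 42/47 = 89%. Without urinalysis: 47 − 12 = 35 and 35 − 5 = 30, or 30/35 = 86%. The count credits the whole differential although only two cell types are tiered. In the other direction, some of the 42 (urine color, for example) may have no natural severity scale, so 42 is a ceiling on the tests that could be graded.

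**2. What the two abnormality tables record.** The documents give no hemoglobin reference limit, so lower limits of 11, 12 and 13 g/dL are assumed. The rule is: low if the value is below the limit, otherwise normal.

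| Baseline → end of treatment (g/dL) | Change | Shift cell at limit 11, 12 or 13 |
|---|---|---|
| 10.5 → 10.4 | 10.4 − 10.5 = −0.1 | low → low |
| 10.5 → 7.0 | 7.0 − 10.5 = −3.5 | low → low |
| 8.1 → 6.0 | 6.0 − 8.1 = −2.1 | low → low |

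All three share one shift cell, and each adds one participant to the out-of-range count at that visit. If the 7.0 occurred at Week 4 and the value was back at 10.5 at end of treatment, the shift cell would still be low → low. A participant who was normal at baseline and dipped at Week 4 would add to the Week 4 out-of-range count, but the depth of the dip would not be recorded. A move from below to above the range would show in the shift table, so the gap concerns movement in the same direction.

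**3. How the SAP treats other safety data.** SAP 18.4.1, 18.5.2 and 18.7.1.1 set markedly abnormal criteria for ECG, vital signs and pulmonary function. SAP 18.4 also plans an ECG shift to the worst post-baseline interpretation. SAP 18.1.1.1 tabulates adverse events by CTCAE v5.0 grade. The general laboratory section has neither grades nor markedly abnormal criteria.

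**The case against.** The strongest reply is that the SAP does what the protocol's own analysis section asks. Protocol 10.12.2 calls for laboratory values to be listed and flagged, with shift tables and analyses of change, and says nothing about grading. SAP 18.3.1 supplies all of that, so on this view no planned graded analysis was dropped and SAP 3.3 had nothing to declare. This stands in part: the mismatch begins between 10.11 and 10.12.2. But 10.11 states the endpoint, and the SAP neither meets its severity part nor says that it will not.

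A second reply is that severity reaches the report through adverse events. Protocol 9.9.7 has the investigator record clinically relevant laboratory changes as adverse events. Protocol 9.9.8.1.5 grades these by CTCAE v5.0, and SAP 18.1.1.1 tabulates maximum severity. That route is real, but it depends on investigator judgement and serves a separate endpoint. Protocol 9.9.7 also sets aside findings linked to the underlying disease unless they are judged worse than expected.

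Third, SAP 6.3 mentions worst-case post-baseline values, and SAP 18.3 bars local results from deriving a laboratory maximum, minimum or worst value, so such values may be intended. Neither section names a graded table. The output shells are not in the documents, so one cannot be excluded there.

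Fourth, the consequence is limited. Safety is descriptive, the study is stopping early, and the mechanism-related lymphocyte counts and the liver tests in the special-interest categories already have tiers. This bears on priority, not on whether the gap exists.

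A reader might go further and infer that worsening is hidden, or that the laboratory endpoint cannot be addressed at all. The documents do not support that. A fall of 3.5 g/dL enters the by-visit change summary, for which SAP Appendix 1 formats minimum and maximum, and it appears in the listings with out-of-range flags.

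**Conclusion.** The point holds in a bounded form. For tests other than lymphocytes, neutrophils, ALT, AST, total bilirubin, ALP and GGT, the severity part of the Protocol 10.11 laboratory endpoint is not tabulated, and SAP 3.3 does not say so. By the Table 5 count this covers 42 of 47 items, or 30 of 35 without urinalysis. The incidence and change-from-baseline parts are planned. What is missing is a count of participants by severity in each treatment group. The change summaries and listings do not give that count, and the adverse event tables give it only for changes that an investigator chose to report.

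It is tempting to turn this into a number of participants per arm who could worsen unseen in the abnormality tables. The documents give no baseline prevalence of abnormal values and no reference limits, and SAP 7 says that the planned 32 per group will not be reached, so no such number is offered. The hemoglobin example is illustrative and depends on the assumed limits. The conclusion also assumes that the output shells add nothing beyond the SAP text. The change is worth making before unblinding, but it touches no efficacy conclusion.

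**What to change.** In SAP 18.3.1, for each laboratory test that has CTCAE v5.0 numeric criteria:
- Add a table of worst post-baseline grade by treatment group.
- Add a shift table from baseline grade to worst on-treatment grade.
- Use central laboratory values, in line with the SAP 18.3 rule on worst values.
- Define a treatment-emergent laboratory abnormality as an increase in grade from baseline.
- List the tests to be graded and define the on-treatment window, so that the derivation is fixed before unblinding.

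Keep the existing reference-range, lymphocyte, neutrophil and liver tables. If the sponsor prefers not to grade laboratory data, SAP 3.3 should at least state that laboratory severity will not be tabulated. That would declare the gap without closing it.

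The cost is SAP wording, grading code applied to data already collected, and two more descriptive tables. CTCAE v5.0 is already the trial's severity scale for adverse events, so no new scale is introduced.

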10.12. Testing Strategy

10.12.1. Efficacy Analysis

The primary analysis of the proportion-based efficacy endpoints will be carried out using the Cochran-Mantel-Haenszel (CMH) method, stratified by (a) naïve to biologic or JAK inhibitor therapy at study entry (yes or no), (b) baseline corticosteroid use (yes or no), and (c) baseline

disease activity (MMS: 4 to 6 or 7 to 9). Results will be expressed as the number of participants in remission, remission percentages, difference in remission percentages, odds ratio, and associated 95% confidence intervals (CIs) and p-values. The stratified CMH analysis will be performed for each etrasimod dose (1 and 2 mg) versus placebo separately. The Cochran-Armitage trend test will also be carried out for all primary and secondary proportion-based efficacy endpoints.

There are multiple null hypotheses for the comparison of etrasimod and placebo in the primary and secondary endpoints. The family-wise Type I error rate will be controlled at a fixed α level at 0.05 (2-sided) using the following testing procedure.

A hierarchical testing procedure will be used to control family-wise Type I error rate at α level 0.05 (2-sided). The comparison of etrasimod 2 mg versus placebo for the primary endpoint (Family 1; F1) is the main gatekeeper. The study is considered positive if F1 is rejected at the α level. Only if this test is significant will etrasimod 2 mg be compared with placebo for all the secondary endpoints (Family 2; F2). The truncated Hochberg method ([Dmitrienko 2011](#), [FDA 2017](#)) will be applied to F2 at α level.

If none of the null hypotheses in F2 is rejected, then testing will stop with all nominal p-values reported for subsequent comparisons of etrasimod 1 mg versus placebo. Otherwise, etrasimod 1 mg will be compared with placebo for the primary endpoint (Family 3; F3) with the unused α from testing F2. Only if this test is significant will etrasimod 1 mg be compared with placebo for all the secondary endpoints (Family 4; F4). The conventional Hochberg method ([FDA 2017](#)) will be applied to F4 with the same unused α for F3. Full details of the efficacy analysis and the hierarchical testing procedure above will be documented prior to database lock in the SAP.

10.12.2. Safety Analysis

All safety data will be listed and summarized by treatment group. All TEAEs will be coded using the latest version of MedDRA and tabulated by System Organ Class and Preferred Term. Incidence of adverse events, SAEs, and adverse events leading to discontinuation will be summarized and presented in descending order of frequency. Associated laboratory parameters such as hepatic enzymes, renal function, and hematology values will be grouped and presented together. Individual participant values will be listed and values outside of the standard reference range will be flagged. Shift tables and analyses of changes from baseline will be produced. The change from baseline for each of the vital signs and 12-lead ECG parameters will be summarized. Incidence of abnormal vital signs parameters and outlier ECG results will be tabulated.

10.13. Interim Analysis

Not applicable

11. ETHICAL CONSIDERATIONS

11.1. Regulatory and Ethical Considerations

This study will be conducted in accordance with the protocol and with the following:

- Consensus ethical principles derived from international guidelines, including the Declaration of Helsinki and CIOMS International Ethical Guidelines;
- Applicable ICH GCP guidelines;
- Applicable laws and regulations, including applicable privacy laws.

The protocol, protocol amendments, ICD, SRSD(s), and other relevant documents (eg, advertisements) must be reviewed and approved by the sponsor, submitted to an IRB/EC by the investigator or designee, and reviewed and approved by the IRB/EC before the study is initiated.

Any amendments to the protocol will require IRB/EC approval before implementation of changes made to the study design, except for changes necessary to eliminate an immediate hazard to study participants.

Protocols and any substantial amendments to the protocol will require health authority approval prior to implementation of changes made to the study design except for changes necessary to eliminate an immediate hazard to study participants.

The investigator will be responsible for the following:

- Providing written summaries of the status of the study to the IRB/EC annually or more frequently in accordance with the requirements, policies, and procedures established by the IRB/EC;
- Notifying the IRB/EC of SAEs or other significant safety findings as required by IRB/EC procedures;
- Providing oversight of the conduct of the study at the site and adherence to requirements of 21 CFR, ICH GCP guidelines, the IRB/EC, European regulation 536/2014 for clinical studies, European Medical Device Regulation 2017/745 for clinical device research, and all other applicable local regulations.

11.2. Reporting of Safety Issues and Serious Breaches of the Protocol or ICH GCP

In the event of any prohibition or restriction imposed (ie, clinical hold) by an applicable regulatory authority in any area of the world, or if the investigator is aware of any new information that might influence the evaluation of the benefits and risks of the study intervention, the Sponsor should be informed immediately.

In addition, the investigator will inform the sponsor immediately of any urgent safety measures taken by the investigator to protect the study participants against any immediate hazard, and of any serious breaches of this protocol or of the ICH GCP guidelines that the investigator becomes aware of.

11.3. Informed Consent

The Investigator will fully inform the subject of all pertinent aspects of the study, including the approval of the study by the IRB/IEC. Before informed consent may be obtained, the Investigator should provide the participant ample time and opportunity to inquire about details of the study and to decide whether to participate.

Prior to a participant's participation in the study, the IRB/IEC-approved ICF must be signed and personally dated by the participant and by the person who conducted the informed consent discussion. If a participant is unable to read, an impartial witness will be present during the entire informed consent discussion.

The written ICF and any other written information to be provided to participants should be revised whenever important new information becomes available that may be relevant to the participant's consent. Any revised written ICF or study materials to be available and/or supplied to participants should receive the IRB/IEC's approval in advance of use. The participant will be informed in a timely

manner if new information becomes available that may be relevant to the participant's willingness to continue participation in the study. The communication of this information should be documented.

During a participant's participation in the study, the participant will receive an updated version of the IRB/IEC-approved signed and dated consent document, as applicable, and any updates to the IRB/IEC-approved written information provided to participants.

11.4. Confidentiality

All information generated in this study is considered highly confidential and must not be disclosed to any person or entity not directly involved with the study unless prior written consent is provided from the Sponsor.

Prior to study participation, the Investigator shall inform the participant that the monitor(s), auditor(s), IRB/IEC, and the regulatory authorities will be granted direct access to the participant's original medical records for verification of clinical study procedures and/or data, and that, by signing a written ICF, the participant is authorizing such access.

In addition, prior to study participation, the participant must be informed that the records identifying the participant will not be made publicly available; if the results of the study are published, the participant's identity will remain confidential.

